#### 4. STUDY ENDPOINTS

# 4.1 Pharmacodynamic (PD) Endpoint

Adverse Event and Vital Signs are considered as the pharmacodynamic endpoints in this study. All other PD endpoints will be considered under safety.

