#### **Study Endpoints**

**Primary Endpoint:** The pharmacodynamics of lasmiditan as measured by serial vital signs, ECGs, and AEs.

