#### Criteria for Evaluation:

Pharmacodynamics: AEs, serial vital signs, ECGs, and physical examination results will be used to assess pharmacodynamics.

Pharmacokinetics: Standard PK parameters (including  $C_{max}$ ,  $t_{max}$ ,  $t_{\%}$ , and AUC [AUC(0-last) and AUC(0-last)]) will be determined using noncompartmental (model independent) methods for lasmiditan from blood samples collected pre-dose and serially following oral administration of study drug during each of the dosing periods (at 0.25, 0.5, 1, 1.5, 2, 2.5, 3, 4, 6, 8, 12, 16, 24 and 30 hours following the dose at time 0 in each dosing period).

Safety: The incidence of adverse events, physical examination findings, measurement of vital signs (BP, HR, respiration rate, and temperature), 12-lead ECG results, and routine clinical laboratory findings (hematology, serum chemistry, and urinalysis) will be used to assess safety. The Drug Effects Questionnaire (DEQ) and Visual Analogue Scales (VAS) will be used as an exploratory assessment of safety.

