## 1.3 Rationale for the Clinical Study

This study will assess the effect of single doses of sumatriptan (Imitrex) 100 mg on the pharmacodynamics of single doses of lasmiditan 200 mg as measured by serial vital signs, ECGs, and adverse events. Safety and tolerability will also be reported.

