#### 8.4.3 ECG Results

All ECG endpoints will be listed by treatment (lasmiditan 200 mg co-administered with sumatriptan (Imitrex) 100 mg, lasmiditan 200 mg co-administered with lasmiditan placebo 200 mg, or sumatriptan (Imitrex) 100 mg co-administered with lasmiditan placebo 200 mg), subject and time of assessment and summarized by descriptive statistics. Changes from baseline in ECG parameters will be summarized by descriptive statistics by dosing sequence.

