#### 6.2.2 PD Population

Pharmacodynamic (PD) population will consist of all subjects who received a single dose of study medication (Lasmiditan or Sumatriptan) and have completed at least one treatment period.

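### The SAP moves ECG from the pharmacodynamic endpoints to safety without a reason, so its PD result covers two of the three components of the protocol's primary endpoint

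*SAP*

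**What the plan says.** The protocol synopsis gives a single primary endpoint: "The pharmacodynamics of lasmiditan as measured by serial vital signs, ECGs, and AEs". Protocol section 1.3 repeats the same three measures, referring to the "pharmacodynamics of single doses of lasmiditan 200 mg as measured by serial vital signs, ECGs, and adverse events". Section 8.4, Pharmacodynamic Analyses, gives ECG its own subsection, 8.4.3, which begins "All ECG endpoints will be listed by treatment" and plans descriptive summaries. Section 8.2.3 bases the primary results on the PD population, and defines that population in the same terms as the safety population.

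The SAP keeps the primary objective but changes what counts as PD. Section 4.1 reads: "Adverse Event and Vital Signs are considered as the pharmacodynamic endpoints in this study. All other PD endpoints will be considered under safety". Section 4.3 lists the 12-lead ECG as a safety assessment. Section 6.4.7 confines the PD analysis to adverse events and vital signs. Section 6.4.10.2 analyses ECG as part of the safety analysis, which section 6.4.10 places on the Safety population. The SAP's section 1, however, still describes the PD effect as measured by vital signs, ECGs and adverse events.

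The SAP also separates the two populations. Under section 6.2.1 any amount of study medication is enough for safety. Under section 6.2.2 the PD population is those who "received a single dose of study medication (Lasmiditan or Sumatriptan) and have completed at least one treatment period".

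**The concern.** An analysis plan should carry the protocol's primary endpoint forward or explain why it does not. Here one component leaves the PD analysis with no explanation, and the SAP's introduction disagrees with its endpoint section. Someone writing the study report could not tell whether ECG belongs to the primary result.

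ECG is not a marginal component. The protocol's introduction presents cardiovascular concern as the factor limiting triptan use, and contrasts lasmiditan with triptans on vasoconstriction. This study gives the two drugs together.

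There is a further gap. The primary objective is comparative: the combination against each drug alone, in a three-period crossover. For ECG the SAP plans summaries by treatment, which leave the reader to subtract one column from another and give no measure of the uncertainty of the difference.

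**Working it through.** **1. Components, side by side**

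| Source | Vital signs | AEs | ECG |
|---|---|---|---|
| Protocol synopsis, primary endpoint | PD | PD | PD |
| Protocol 1.3, rationale | PD | PD | PD |
| Protocol 8.4, PD analyses | PD (8.4.2) | PD (8.4.1) | PD (8.4.3) |
| SAP 1, introduction | PD | PD | PD |
| SAP 4.1, PD endpoint | PD | PD | safety |
| SAP 6.4.7, PD analysis | PD | PD | not included |

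The primary endpoint has 3 components, the SAP's PD set has 2, and ECG is the one missing. The protocol's evaluation criteria go wider: "AEs, serial vital signs, ECGs, and physical examination results will be used to assess pharmacodynamics". The SAP also moves physical examination to safety, but that is not part of the stated primary endpoint, so two of three is the right count.

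**2. Is any ECG analysis lost?**

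Protocol Table 2 schedules a pre-dose ECG and recordings at 1, 1.5, 2, 2.5, 4, 8 and 24 hours, which is 1 + 7 = 8 per period. Over 3 periods and 42 subjects this is 8 × 3 × 42 = 1,008 scheduled recordings. SAP 6.4.10.2 covers the same schedule. It gives observed values and change from baseline per treatment at each time, counts of the overall interpretation, a shift table and a listing. None of the 1,008 is removed from analysis. Protocol 8.4.3 asked only for listings and descriptive statistics, with changes shown by dosing sequence. For a comparison of treatments the SAP's layout is the more useful.

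**3. Analysis set**

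- Safety (SAP 6.2.1): anyone dosed.
- PD (SAP 6.2.2): dosed, with at least one period completed.
- Difference: subjects dosed who completed no period.

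The documents do not predict that number. If attrition is as planned (42 enrolled, 36 completing), it lies between 0 and 42 − 36 = 6, or 0 to 14.3% of 42. Reaching 6 would need every drop-out to occur after dosing in the first period, so the true figure is probably near the lower end.

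The SAP also leaves open which set applies. Section 6.2.2 does not say which analyses use the PD population, and section 6.4.7 names none. Section 6.4.10 lists adverse events and vital signs, as well as ECG, among the parameters analysed on the Safety population.

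**4. What a direct comparison would involve**

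A is lasmiditan alone, B sumatriptan alone and C both. Y(X,t) is a subject's ECG value under treatment X at hour t, with t = 0 for pre-dose. The time-matched difference is

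d(C−A, t) = [Y(C,t) − Y(C,0)] − [Y(A,t) − Y(A,0)], and likewise for C−B.

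The SAP already defines baseline within each period, so nothing new has to be collected. With n subjects contributing, a paired 90% interval has half-width t(0.95, n−1) × SD(d)/√n. At n = 36 this is 1.690 × SD(d)/6 = 0.28 SD(d). The documents give no SD for any ECG parameter, so the width in milliseconds or beats per minute cannot be stated.

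Number of intervals: 7 parameters (HR, RR, PQ/PR, QRS, QT, QTcF, QTcB) × 7 post-dose times × 2 contrasts = 98. At 90% confidence, 98 × 0.10, or about 10, would be expected to miss their true value by chance.

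**The case against.** The strongest reply is that this is a change of heading. The protocol itself classifies ECG twice, in the primary PD endpoint and in the secondary safety endpoint. SAP 4.1 states its handling openly and still calls the moved items PD endpoints. ECG ends up with fuller output than vital signs, which stayed under PD. Neither document sets a hypothesis, margin, alpha or success rule for ECG, so no test is lost. The protocol's section 8 leaves detailed methods to the SAP and requires departures from the planned analyses to be justified in the study report. Differences with confidence intervals are not in the protocol's ECG plan, and the SAP does not give them for vital signs either.

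Most of this stands. The data and descriptive tables survive, and the within-subject differences are an addition, not the restoration of something promised.

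Three things do not fall to it. A second classification as safety does not cancel the first as primary PD. The SAP's introduction and its section 4.1 cannot both be right. And a justification written in the study report comes after the results, whereas the definition of the primary result should be settled before database lock.

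**Conclusion.** The mismatch is real and should be corrected. The SAP's PD result omits one of the three components of the primary endpoint, gives no reason, and contradicts the SAP's introduction. It may rest on a slightly different set of subjects from the ECG tables. It also gives no direct within-subject ECG comparison, although the objective is comparative.

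A reader might infer three stronger things that the documents do not support:

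- *That the cardiac data are dropped.* They are not. The 1,008 figure counts recordings that SAP 6.4.10.2 still summarises and lists; it does not measure lost information.
- *That the components are bound to be on different denominators.* The SAP also puts adverse events and vital signs on the Safety population, so a common set exists. That PD analyses use the narrower set is an inference from protocol 8.2.3, and the sets differ only by subjects dosed who completed no period.
- *That relabelling alone changes what the trial can conclude.* With no decision rule, the same tables support the same descriptive reading under either heading.

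The bound of 6 subjects assumes that attrition does not exceed the plan. The practical effect is on clarity, on what is reported as primary, and on how directly the crossover answers its question.

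**What to change.** 1. In SAP 4.1 and 6.4.7, restore ECG as a PD endpoint, with HR, RR, PQ/PR, QRS, QT, QTcF and QTcB. This also brings those sections into line with the SAP's introduction.
2. State one population for all three PD components. Since protocol 8.2.3 defines the PD and safety populations identically, using that single definition is the simplest course.
3. Add the time-matched within-subject differences C−A and C−B in change from pre-dose, with 90% confidence intervals, and report how many subjects contribute to each. Protocol 8.3 allows 90% intervals. Label them as estimation, with no success rule and no multiplicity adjustment.
4. Keep the ECG outputs in SAP 6.4.10.2 as they are.

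If the sponsor prefers to leave ECG under safety, the minimum is a stated reason for departing from the protocol's primary endpoint and a matching correction to the SAP's introduction. That would still leave the comparative gap.

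The cost is some SAP wording and a few extra tables from data already being collected. The drawback is the 98 or so unadjusted intervals, which must be read as description: an isolated interval excluding zero should not be taken as evidence of an interaction.

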# 4.2 Pharmacokinetic (PK)Endpoints

Pharmacokinetic endpoints will include:

- Cmax maximum measured plasma concentration
- Tmax time to reach maximum measured plasma concentration
- AUC(0-tlast) area under the plasma concentration versus time curve from time 0 to last measurable concentration.

- AUC(0- $\infty$ )- area under the plasma concentration versus time curve from time 0 to infinity
- $t_{1/2}$  terminal phase half-life.
- CL/F- Apparent total clearance of the drug from plasma.
- Vz/F- Apparent volume of distribution during terminal phase.
- $\lambda_z$  terminal rate constant.

These PK parameters will be derived from Lasmiditan plasma concentration, Sumatriptan plasma concentration as well as the combination of Lasmiditan and Sumatriptan versus time curves following dosing on Day 1 (pre-dose and 0.25, 0.5, 1, 1.5, 2, 2.5, 3, 4, 6, 8, 12, 16, 24 and 30 h following the dose at time 0 in each dosing period).

## 4.3 Safety Endpoints

Safety will be assessed by physical examinations, standard 12-lead ECGs, clinical laboratory tests (clinical chemistry panel, CBC, and urinalysis), Columbia Suicide severity rating scale (C-SSRS), DEQ-5, Visual Analogue scales (VAS) and collection of adverse events.

## 5. **DEFINITIONS**

# AUC(0-tlast)

Area under the concentration-time curve from time zero (pre-dose) to time t of the last quantifiable concentration of each dose of Lasmiditan, Sumatriptan or (Lasmiditan+Sumatriptan) calculated by means of the mixed log-linear trapezoidal rule.

# $\mathrm{AUC}_{(0-\infty)}$

Area under the plasma concentration vs. time curve from time 0 to infinity, calculated as AUC = AUC0-t + AUCextra. AUCextra represents an extrapolated value obtained by C / $\lambda z$ , where C is the predicted concentration at time t at or above LOQ, and  $\lambda z$  is the estimated apparent terminal rate constant.

#### %AUCextrap

Area under the plasma concentration-time curve extrapolated from time t to infinity as a percentage of total AUC.

### Cmax

Maximum concentration in plasma following each dose of Lasmiditan, Sumatriptan or (Lasmiditan+Sumatriptan), obtained directly from the observed concentration versus time data.

## $\lambda_{z}$

Apparent terminal elimination rate constant, determined from the slope of the log-transformed plasma concentration curve.

#### CL/F

Apparent total clearance of the drug from plasma.

#### Vz/F

Apparent volume of distribution during terminal phase.

#### $t_{1/2}$

Apparent terminal elimination half-life , is determined as  $ln(2)/\lambda_z$ .

#### Tmax

Time to maximum plasma concentration.

## **Study Day**

This is the number of days from the date of the first study drug administration:

Study Day = (Target Date - Date of the first study drug administration) + 1 if target date is greater than or equal to the date of the first study drug administration or

Study Day = (Target Date - Date of the first study drug administration) if target date is less than date of the first study drug administration.

#### **Baseline**

Baseline is defined as the latest assessment prior to the first study drug administration within each period unless otherwise specified. If the assessment occurs on the same date as the dose administration, then the time of assessment should be compared to the time of dose administration. If time is not available, protocol schedule of events should be considered.

## 6. STATISTICAL METHODOLOGY

#### 6.1 General Considerations

All pharmacokinetic evaluations will be performed using non-compartmental methods in Phoenix® WinNonlin® version 6.4 or higher (Pharsight Corporation, Mountain View, California, USA). All statistical evaluations will be conducted using SAS® version 9.3 or higher (SAS® Institute, Cary, North Carolina). All tables, figures and listings will be produced in landscape format.

The term "study drug" may refer to either Lasmiditan or Sumatriptan (or both Lasmiditan and Sumatriptan together).

In general, all data will be listed by subject, period, treatment and visit/time point where appropriate. The total number of subjects in the study group (N) under the stated population will be displayed in the header of summary tables.

Data will be summarized using descriptive statistics for continuous variables. Unless otherwise specified, descriptive statistics will include number of subjects, mean, standard deviation, minimum, median and maximum. In case of n<2, where n indicates the number of evaluable subjects at the particular time point, the standard deviation will be empty. The minimum and maximum statistics will be presented to the same number of decimal places as the original data. The mean and median will be presented to one more decimal place than the original data, whereas the standard deviation will be presented to two more decimal places than the original data.

In summary tables of categorical variables, counts and percentages will be used. The count [n] indicates the actual number of subjects with a particular value of a variable or event, which should always be less than or equal to the total number of subjects with non-missing value of the variable or event in the respective study group [M].

Percentage will be obtained by: % = (n/M)\*100. Unless otherwise stated, all percentages will be expressed to one decimal place.

The closest non-missing measurement (whether from scheduled or unscheduled visit) taken prior to the first study drug administration within each period will be considered as the baseline value. The change from baseline values will be derived for each subject as the post-baseline evaluation minus the baseline evaluation within each period.

All dates will be displayed in DD/MMM/YYYY format.

## 6.2 Analysis Populations

The analysis populations defined in this study are as follows:

#### **6.2.1** Safety Population

Safety population will consist of all subjects who received any amount of study medication (Lasmiditan or Sumatriptan). The safety population will be used for all safety analyses.

#### 6.2.2 PD Population

Pharmacodynamic (PD) population will consist of all subjects who received a single dose of study medication (Lasmiditan or Sumatriptan) and have completed at least one treatment period.

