## 8.2.3 Analysis Populations

Pharmacodynamic population: All randomized subjects who received at least one dose

of any study drug.

Safety population:

All randomized subjects who received at least one dose

of any study drug.

Pharmacokinetic population:

All subjects with evaluable PK data will be included in the pharmacokinetic population. Subjects with incomplete PK data, e.g. data missing from one entire study period, will be listed and the derived PK parameters will not be

considered for summary statistics and analytical

evaluations.

The primary results will be based on the pharmacodynamic population. All safety analyses will be based on the safety population.

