#### 6.4.7 Pharmacodynamic Analysis

Pharmacodynamic analysis will involve the analysis of all adverse events (AE) and the analysis of vital signs. All AEs and vital signs data will be listed and summarized.

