#### 6.4.8 Pharmacokinetic Analysis

Calculation of PK parameters will be performed using Phoenix® WinNonlin® version 6.4 (or later). Statistical analysis and generation of summary tables and listings will be performed in SAS.

All PK analyses will be performed on the PK population.

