## 6.4.10 Safety Analysis

All safety data will be listed and tabulated. The analysis will be performed on the Safety population.

Safety parameters include adverse events, laboratory parameters, vital signs, ECG, physical examination findings, C-SSRS and DEQ-5 and VAS.

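### SAP 6.2.2 adds a completion condition to the protocol's PD population, and SAP 6.4.7 does not say which population the primary AE and vital-sign tables use

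*SAP*

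**What the plan says.** Protocol 8.2.3 defines the PD population as "All randomized subjects who received at least one dose" of any study drug, and defines the Safety population identically. It then states: "The primary results will be based on the pharmacodynamic population".

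SAP 6.2.2 defines the PD population as "all subjects who received a single dose of study medication (Lasmiditan or Sumatriptan) and have completed at least one treatment period". It gives no reason for the added condition and does not define completion of a period. SAP 6.2.1 has no such condition: any quantity of either drug puts a subject in the Safety population.

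SAP 6.1 makes table denominators depend on a named population: "The total number of subjects in the study group (N) under the stated population will be displayed in the header of summary tables". The PK section names one ("All PK analyses will be performed on the PK population", SAP 6.4.8), and so does the safety section ("The analysis will be performed on the Safety population", SAP 6.4.10). The PD section says "Pharmacodynamic analysis will involve the analysis of all adverse events (AE) and the analysis of vital signs", but neither that statement nor the AE and vital-sign text below it names a population. SAP 6.4.10 lists AEs and vital signs again, as safety parameters, but has no AE or vital-sign subsection. The only detailed specification of those tables is therefore in SAP 6.4.7.

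**The concern.** The SAP definition removes subjects whom the protocol includes in its primary analysis set, so it is a change and not added detail. Because SAP 6.4.7 is silent, a programmer could run the primary tables on the SAP 6.2.2 population or on the Safety population, and both choices could be defended from the text.

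The condition can also depend on the outcome. SAP 4.1 makes AEs and vital signs the PD endpoints. Protocol 4.4 lists an AE as a reason for withdrawal, and protocol 7.6 and 7.7 allow discontinuation after clinically significant vital-sign findings. A subject who leaves during Period 1 for such a reason would be missing from the table intended to report it. Protocol 4.4 mentions replacement only for subjects who discontinue before dosing in Period 1, so it provides no replacement for a dosed early stopper.

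**Working it through.** The plan gives no figure for the size of the PD population, so there is none to reproduce. Its one power statement concerns PK equivalence and does not bear on this point.

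**1. The definitions side by side**

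| Source | Must be dosed | Must complete a period | Use stated |
|---|---|---|---|
| Protocol 8.2.3, PD | yes | no | primary results |
| SAP 6.2.1, Safety | yes | no | safety analyses |
| SAP 6.2.2, PD | yes | at least one | none |

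In substance, the SAP Safety population matches the protocol's PD population. The SAP PD population does not.

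**2. Who is affected.** Only subjects who are dosed in Period 1 and complete no period. Someone who completes Period 1 and stops later stays in under either definition. If all 42 planned subjects are dosed and k of them stop in this way, N is 42 under the protocol and 42 − k under SAP 6.2.2. The plan allows for 42 − 36 = 6 losses overall. If all six were of this kind, N would be 36.

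**3. What data such a subject may have.** Post-dose supine vital signs are taken at 1, 2, 4, 8 and 24 hours (five readings) and orthostatic readings at 1 and 2 hours (two), per protocol 7.6 and 7.7. Suppose completion means staying to discharge, at least 30 hours after dosing (protocol 5.4.2).
- A subject followed for the 4 hours that protocol 4.4 seeks after withdrawal has 3 of 5 supine and 2 of 2 orthostatic readings.
- A subject who leaves after the 24-hour reading has 5 of 5 and 2 of 2.

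Both would be excluded, the second with a full set of vital signs.

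**4. Effect on a TEAE rate.** Let M be the number who received a treatment, including one early stopper, and p the TEAE rate in the other M − 1. Let e = 1 if the stopper had a TEAE and 0 if not.
- Rate under SAP 6.2.2: p
- Rate under protocol 8.2.3: ((M − 1)p + e)/M
- Protocol minus SAP: (e − p)/M, never larger in size than 1/M

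The bound is 1/42 = 2.38 points, or 1/36 = 2.78 points if only 36 receive that treatment. With M = 42:

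| p | e | Protocol | SAP | Difference (points) |
|---|---|---|---|---|
| 50% (assumed) | 1 | 51.19% | 50.00% | +1.19 |
| 86% | 1 | 86.33% | 86.00% | +0.33 |
| 50% (assumed) | 0 | 48.81% | 50.00% | −1.19 |
| 86% | 0 | 83.95% | 86.00% | −2.05 |

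The 86% is the 200 mg rate in the Phase 2 migraine study (protocol 1.2), used here only as an illustration.

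**5. More than one stopper.** Assume 21 of 42 subjects have a TEAE on the combination, and that the early stoppers all took the combination in Period 1 and all had one. Three stoppers change the rate from 21/42 = 50.0% to 18/39 = 46.2%. Six change it to 15/36 = 41.7%. These are stress cases, not forecasts.

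**6. A single event type.** If an event occurs only in one early stopper, its row changes from 1/42 = 2.4% to 0/41 = 0%. The shift in the overall rate is small, but the event disappears from the primary table.

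**The case against.** The strongest reply is that the intended population is easy to infer: the SAP defines a PD population, has a pharmacodynamic analysis section, and the protocol ties the primary results to the PD population. That inference is reasonable, but it does not settle the matter, because the two documents define the population differently and SAP 6.4.10 also claims both endpoints for the Safety population.

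It can also be said that running the tables on the Safety population does no harm, since that set agrees in substance with the protocol's PD set. Even under SAP 6.2.2, SAP 6.4.10 promises that all safety data, including AEs and vital signs, will be tabulated on the Safety population. Both points are correct and limit the damage. They leave the primary tables undefined.

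Early exit is also unlikely. Each period is one supervised dose followed by confinement. Discontinuation after a finding need not mean leaving before discharge, and protocol 5.4.2 allows a subject with persisting AEs to stay in the unit. Protocol 1.2 reports no AE withdrawals in lasmiditan development and a food-effect study in which all 30 healthy subjects completed. Protocol 1.4 reports no AE withdrawals in Phase 1 at up to 400 mg. This supports an expected count near zero. It does not cover the combination with sumatriptan, and the protocol allows the withdrawals that would trigger the problem.

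Finally, protocol section 8 assigns the justification of deviations to the study report, so an unflagged change in the SAP breaches no stated rule. That is accepted. The objection here is to the conflict itself, which is easily missed when nothing marks it.

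**Conclusion.** The concern holds. SAP 6.2.2 conflicts with protocol 8.2.3 on the population for the primary results, its added condition can select on the outcome, and SAP 6.4.7 does not say which population applies.

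The consequence is modest. It is zero if every dosed subject completes Period 1. Otherwise each excluded subject moves the TEAE rate of the treatment received by at most 2.4 points with 42 treated, or 2.8 with 36, upward or downward depending on whether that subject had a TEAE. The AE and vital-sign outputs in the SAP are descriptive, so no pass/fail conclusion changes. The excluded subject's data remain in the listings and the Safety population, and the disposition table (SAP 6.4.1) shows the size of each population. The bound does not depend on the true TEAE rate. The worked examples do, and they assume 42 treated. The 30-hour reading of completion is also an assumption, because the SAP gives no definition.

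This should be corrected, but it does not threaten the trial's conclusions.

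**What to change.** In SAP 6.2.2, replace the definition with the protocol's, "All randomized subjects who received at least one dose" of any study drug, and delete the completion condition. This also removes the reference to a single dose, which could be misread as exactly one dose in a three-period crossover.

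In SAP 6.4.7, state that the AE and vital-sign PD analyses use this population.

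As a separate clarification that is not part of the population definition, say that summaries are by treatment received and use whatever post-dose data exist, keeping the present rule that a time point counts only subjects with both baseline and that value.

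The cost is two sentences in the SAP, plus one for the clarification. No extra data are collected. At most a few partial profiles enter the PD tables, and the existing time-point rule already handles partial vital-sign data.
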